1.3.4.3 External Ocular Examination

The motility of the extraocular muscles and the appearance and function of the eyelids will be assessed at Month 24 and 30, and recorded as: Normal, Abnormal Non-Clinically Significant, Abnormal Clinically Significant.

1.4 Study Data

The study data to be analyzed include data carried over from the NGF0120 study, all clinical data captured by eCRF, as well as external data per data transfer agreements. The eCRF database will be locked for the final analyses.

Final data from the NGF0120 study will be integrated to the NGF0122 study for analysis as applicable, such as summaries of demographic and baseline characteristics, and change from baseline results.

2 GENERAL ANALYSIS DEFINITIONS

All analysis dataset preparations and statistical analyses will be performed using SAS® version 9.4 (SAS/STAT 15.1) or higher. Listings for CSR Appendix 16.2 will include, as a minimum, all the subject data points to be used for analyses. Data listings will be provided for all enrolled subjects with data available.

2.1 Study Eye

The study eye designated in the study NGF0120 will be used for this study. It will be clearly identified in the listings when the assessments involve both eyes.

2.2 Study Period, Visit, and Day

The study period, visit, and day will be integrated across the NGF0120 and NGF0122 studies, and will consist of screening, baseline (Day -1), treatment (Week 2, Week 4, Week 8), follow-up (Week 32), extended follow-up Month 24 or Week 96, and extended follow-up Month 30 or Week 120.

A reference date refers to the date of the first study product administration in the study NGF0120. All safety and efficacy assessments at all visits will be assigned a day relative to this date. The relative day will be defined as:

- visit date – reference date + 1 for visits on or after the reference date, and
- visit date – reference date, for visits before the reference date.

2.3 Definition of Baseline

In general, the baseline is defined as the last assessment before the first study product administration in the study NGF0120 unless specifically stated otherwise.

2.4 Out of Window and Unscheduled Visits

All scheduled assessments after first administration of randomized study product will be used. The protocol defined windows for scheduled visits will not be used in the analyses by visit. Data will be assigned to the scheduled visit closer in time to the scheduled visit. Unscheduled visit data will only be used in an analysis if there is no other available data closer in time to a scheduled visit. All unscheduled visit data will be included in data listings.

2.5 Analysis Population

The full analysis set (FAS) will include all enrolled patients who attended either 24-Month Study Visit, or 30-Month Study Visit, or both. The FAS will be used for both efficacy and safety analyses.

2.6 Unit of Analysis

In general, the unit of analysis will be study eye (affected eye) for eye-level summary, and subject for subject-level summary. Data for both eyes will be presented in the data listings.

2.7 Definition of Subgroups

No subgroup analyses are planned.

2.8 Descriptive Summaries

Summary statistics and statistical analyses will be performed only for subjects included in the relevant analysis population. For the calculation of summary statistics and statistical analysis, unrounded data will be used. For endpoints that are continuous in nature: number of observations, mean, median, 25th and 75th quartiles, minimum and maximum, and standard deviation (SD) values will be presented as descriptive statistics summary for both observed values and change from baseline values at each scheduled visit if applicable. For endpoints that are categorical in nature: frequency counts and percentages will be presented as descriptive statistics summary at each scheduled visit if applicable. The number of subjects / eyes with available data (n) will also be reported.

The number of decimal places to display for calculated data will be determined by the original scale of the data. Means and medians will be reported with one (1) additional decimal place. Standard deviation will be reported with two (2) additional decimal places. Minimum and maximum will be reported with the same number of significant digits as the method of capture.

2.9 Type 1 Error Control for Multiple Tests

Not applicable. This is an exploratory, hypothesis generating study. All efficacy analyses are considered exploratory and all statistical tests will be descriptive in nature with no need for control of type 1 error.

2.10 Handling of Missing Data

The primary efficacy analysis will be based on observed cases (i.e. no missing data imputation).

All analyses unless specified will be conducted on an as observed case basis, that is, no further imputation of missing data will be carried out unless explicitly stated otherwise.

In the descriptive summaries, the number of subjects with missing data will be presented under the “Missing” category. Summary statistics for continuous variables will be calculated only on non-missing values. For categorical variables, missing values will be reported under the “Missing” category but not included in the denominator count when computing percentages. When continuous data will be summarized, only the non-missing values will be evaluated for computing summary statistics. Any exception will be declared.

Imputation for Missing Concomitant Medication and AE Start and Stop Days:

Missing and/or incomplete dates for concomitant medications and AEs will be imputed for calculating Start/Onset Day and Stop Day only. The Start/Onset Day and Stop Day may be used for calculating prior or concomitant medications or calculating treatment emergent AEs. Missing and/or incomplete dates will be imputed in a manner that assumes the worst case scenario (i.e. Start/Onset as close as possible to the First Study Treatment Administration and stopped such that it assumed to have lasted for the longest possible duration, taking into account that the Start/Onset date should not be after the Stop date).

Imputation for missing Stop Date:

- For a completely missing stop year (regardless of day or month) the medication/AE will be assumed to be ongoing.
- For a missing stop month (and a medication/AE that is not ‘Ongoing’) the medication/AE will be assumed to have ended the last available month of that year.
- For a missing stop day (and a medication/AE that is not ‘Ongoing’) the medication/AE will be assumed to have ended on the last day of the month if the month is available.

Imputation for missing Start/Onset Date:

- For a completely missing Start/Onset date (day, month and year), the Start Day of medication/AE will be considered pre-treatment (i.e. prior) if the stop date or partial stop date concludes the medication/AE was stopped before the first administration of the study product. In all other instances (i.e. inconclusive stop date or Ongoing medication/AE) the Start Day of medication/AE will be assumed to have started at the date of the first administration of the study product (i.e. assumed to be concomitant or treatment emergent as is applicable).

- For a missing start/onset month the medication/AE will be assumed to have started in January of that year, or at the date of first administration of the study product if the start/onset year was the same as the year of first administration of the study product.
- For a missing start/onset day the medication/AE will be assumed to have started on the first day of the month, or at the date of first administration of the study product and the year was the same as the Randomization month and year.

3 SUBJECT INFORMATION

In general, all subject information will be summarized for the FAS Population, unless stated otherwise.

3.1 Disposition Information

Summaries will be provided for number and percentage of completed or discontinued study with the reasons of discontinuation as collected on eCRF.

3.2 Study Visits

The number and percentage of subjects completing each scheduled visit will be tabulated.

3.3 Demographics Characteristics

Descriptive statistics or frequency tabulation will be provided for age, gender, race, and ethnicity based on the data extracted from the Study NGF0120.

3.4 Etiology of Neurotrophic Keratitis

The etiology of neurotrophic keratitis will be included in a listing.

3.5 Medical and Ocular History and Surgical Procedures

A summary table will be prepared for the medical history/surgical procedure data, and one for ocular history/surgical procedure data. Conditions will be categorized according to Medical Dictionary for Regulatory Activities (MedDRA)-coded terms. This table will indicate the number and percentage of subjects who presented with previous history overall and by system organ class (SOC) and preferred term (PT). SOC will be sorted alphabetically and PT within each SOC will be sorted by overall descending order of frequency.

3.6 Protocol Deviations

All reported protocol deviations will be documented and included in the CSR. All reported protocol deviations and inclusion or exclusion exceptions will be included in a listing.

4 CONCOMITANT MEDICATIONS CCI

All reported medications will be coded using World Health Organization-Drug Dictionary (WHO-DD). For summary of medications, the coded anatomical main

group (ATC) level 1 and ATC level 4 will be sorted by alphabetical order, and generic medication name (Preferred Term) will be sorted by overall descending order of frequency.

Concomitant medications include all medications that a subject used during the study on or after the first administration of the study product.

Summary tables will be prepared for the reported use of all concomitant medications including ATC by generic name within ATC level 1 and ATC level 4, and location (ocular vs non-ocular) during the entire extended follow-up period.

Summary tables will be provided for CCI [REDACTED] non-ocular medications, which will be determined by medical review of the medications on the final data at the end of study.

5 ANALYSIS OF EFFICACY

All efficacy analyses will be considered exploratory and performed based on the observed cases in the FAS population. No missing data imputation will be considered.

For continuous efficacy endpoints, descriptive statistics of the observed and change from baseline will be tabulated by visit where that endpoint is assessed. Where appropriate, the asymptotic 95% confidence intervals of mean change from baseline will be presented as well as p values from one-sample t-test and Wilcoxon signed rank test (depending on the distribution of the data) to compare the observed values vs baseline.

For responder/categorical efficacy endpoints, analyses will include percentage of responders/categorized results, and associated exact (Clopper-Pearson) 95% confidence intervals where appropriate as well as p values from a binomial test to assess that responder rates are greater than zero.

- Percentage of patients who had corneal epithelial healing at Week 8 in the DEFENDO Study, who maintain healing at Month 24 and Month 30 of the long-term follow-up

The patients who had corneal epithelial healing at Week 8 and maintain healing at Month 24 and Month 30 will be summarized as a binary goal attainment variable (Yes/No) based on the subset of patients who achieved corneal epithelial healing at Week 8, as determined by the CRC.

- Percentage of patients who did not have corneal epithelial healing at Week 8 in the DEFENDO Study who have a healed corneal epithelium at Month 24 and Month 30 of the long-term follow-up

The patients who did not have corneal epithelial healing at Week 8 and who have corneal epithelial healing at Month 24 and Month 30 will be summarized as a binary goal attainment variable (Yes/No) based on the subset of patients who did not have corneal epithelial healing at Week 8, as determined by the CRC.

- Percentage of patients who achieved an improvement in corneal sensitivity at Week 8 in the DEFENDO Study who still have improvement in corneal sensitivity at Month 24 and Month 30 of the long-term follow-up

The improvement in corneal sensitivity is defined as change from baseline > 0 (cm) of the study eye. The patients who achieved an improvement in corneal sensitivity at Week 8 and still have improvement in corneal sensitivity at Month 24 and Month 30 will be summarized as a binary goal attainment variable (Yes/No) based on the subset of patients who achieved an improvement in corneal sensitivity at Week 8.

- Percentage of patients who did not achieve an improvement in corneal sensitivity at Week 8 in the DEFENDO Study who have improvement in corneal sensitivity at Month 24 and Month 30 of the long-term follow-up

The patients who did not achieve an improvement in corneal sensitivity at Week 8 and who have improvement in corneal sensitivity at Month 24 and Month 30 will be summarized as a binary goal attainment variable (Yes/No) based on the subset of patients who did not achieve an improvement in corneal sensitivity at Week 8.

- Mean change in corneal sensitivity from baseline and Week 8 at Month 24 and Month 30

The corneal sensitivity (cm) in the NEI zone of the study eye as measured by the Cochet-Bonnet aesthesiometer will be summarized as a continuous variable.

- Schirmer I change from baseline and Week 8 to Month 24 and Month 30

The Schirmer tear test result (mm) in the study eye will be summarized as a continuous variable.

- TFBUT change from baseline and Week 8 to Month 24 and Month 30

The average TFBUT result (sec) of two repeat measurements in the study eye will be summarized as a continuous variable.

- Mean change in BCDVA from baseline and Week 8 to Month 24 and Month 30

The logMAR visual acuity score in the study eye will be summarized as a continuous variable.

- Percentage of patients that achieve a 15-letter gain from baseline and Week 8 in BCDVA at Month 24 and Month 30

The patients that achieve a 15-letter gain in BCDVA will be determined based on $\text{logMAR} - \text{Baseline logMAR} \leq -0.3$. It will be analyzed using a binary goal attainment variable (Yes/No).

- IDEEL change from baseline and Week 8 at Month 24 and Month 30

Subscores will be derived for the following modules and will be calculated only if at least 50% of the items of the dimension are completed; otherwise, the scores are missing.

Module 1:

Dry eye impact on daily life (27 questions) comprising 3 QoL domains: 1.a “Daily activities limitations”, 1.b “Emotional wellbeing” and 1.c “Work limitations”. 26 questions will be considered as part of one of these 3 domains. Question 22 will not be considered part of a domain.

1.a: Daily Activities

Daily activities section	Used in calculation of domain score?
1. Doing close work in the morning or afternoon (such as crossword puzzles, reading, looking at a computer, and/or sewing)	Yes
2. Doing close work in the evening or at night	Yes
3. Driving	Yes
4. Being around and/or using scented products (such as cologne or hairspray)	Yes
5. Working on a computer	Yes
6. Going somewhere where there is tobacco smoke or being around someone who smokes	Yes
7. Wearing contact lenses	No
8. Wearing make-up near or on my eyes	No
9. Flying on an airplane	No

Response for questions 1 to 9	Original response code	Item score
I did not do this activity for reasons other than my dry eyes	1	5
None of the time	2	5
A little of the time	3	4
Some of the time	4	3
Most of the time	5	2
All of the time	6	1
I can no longer do this activity due to my dry eyes	7	0

The response option “I did not do this activity for reasons other than my dry eyes” has a response coded 1 but a scored item value of 5. The original response code is the value to be used for data-entry. The item score is used during the computation of the Daily Activity Limitations Scale Score. Higher item scores are intended to reflect better quality of life (i.e. less limitations on daily activities). Only the first 6 questions are included in the Daily activity Limitations scale score. Questions 7, 8 and 9 are excluded. If 50% (3) or fewer of the 6 questions used in calculating Daily Activity Limitations score have missing item score, then the scale score is calculated by multiplying the mean of the non-missing item score by 20. If 4 or more of the 6 item scores are missing, then the scale score is not calculated and should be set at missing. Multiplying by 20 transforms the scale score to a 0 to 100 scale, with 0 reflecting the greatest degree of limitations on daily activities measurable by the scale and 100 reflecting the greatest freedom from limitations on daily activities.

1.b Feelings

Feelings	Used in calculation of domain score?
10. Irritability	Yes
11. Impatience	Yes
12. Feeling sad	Yes
13. Worry that my dry eyes will get worse	Yes
14. Feeling annoyed	Yes
15. Feeling like my eyes do not look nice	Yes
16. Feeling like I have to make adjustments to my life	Yes
17. Feeling different from other people because of my dry eyes	Yes
18. Feeling like I am always aware of my eyes	Yes
19. Feeling older than I really am	Yes
20. Feeling like people look at me and think I am fine when I'm not	Yes
21. Feeling like there is nothing I can do for my dry eyes	No

Response for questions 10 to 21	Original response code	Item score
None of the time	1	4
A little of the time	2	3
Some of the time	3	2
Most of the time	4	1
All of the time	5	0

11 questions are included in the Emotional Well-Being score. Question 21 (IDLEMO12) is excluded from calculation. If 50% (5) or fewer of the 11 questions used in the calculation of Emotional Well-Being score have missing item score, then the scale score is calculated by multiplying the mean of the non-missing item scores by 25. If 6 or more of the 11 item scores are missing, then the scale score is not calculated and should be set at missing. Multiplying by 25 transforms the scale score to a 0 to 100 scale, with 0 reflecting the worst level of emotional well-being measurable by the scale and 100 reflecting the best.

1.c Work

Work	Used in calculation of domain score?
22. Are you currently working?	-
23. Feeling distracted	Yes
24. Feeling like I couldn't concentrate	Yes
25. Having to take a break from work	Yes
26. Having to change the way I work (such as the way I read, look at a computer, or work outside)	Yes
27. Having to change my work environment (such as how close I am to an air conditioning or heating vent)	Yes

Response for question 22	Original response code	Item score
Yes	1	1
No	2	0

Response for questions 23 to 27	Original response code	Item score If Response for question 22=0	Item score If Response for question 22=1
None of the time	1	Missing	4
A little of the time	2	Missing	3
Some of the time	3	Missing	2
Most of the time	4	Missing	1
All of the time	5	Missing	0

5 questions are included in the Work Limitations domain. If 50% (2) or fewer of the 5 questions used in the calculation of the Work Limitations score have missing item scores, then the scale score is calculated by multiplying the mean of the non-missing item scores by 25. If 3 or more of the 5 item scores are missing, then the scale score is not calculated and should be set to missing. Multiplying by 25 transforms the scale score to a 0 to 100 scale, with 0 reflecting the greatest degree of limitation at work measurable by the scale and 100 reflecting the least limitation at work.

Module 2:

Dry eye Treatment satisfaction & Bother module (10 questions) comprising 2 QoL domains: 2.a “Satisfaction with Treatment Effectiveness” and 2.b “Treatment-Related Bother/Inconvenience”.

2.a Satisfaction with Treatment Effectiveness

Satisfaction with Treatment Effectiveness	Used in calculation of domain score?
1. OVER THE LAST TWO WEEKS , how often did you use treatment for your dry eyes?	-
2. I was happy with how quickly my treatments worked	Yes
3. I was happy with how long the effects of my treatments lasted	Yes
4. The treatments I used completely eliminated my dry eye symptoms	Yes
5. The treatments I used relieved most of my dry eye symptoms	Yes

Response for question 1	Original response code	Item score
None of the time	1	0
A little of the time	2	1
Some of the time	3	2
Most of the time	4	3
All of the time	5	4

Response for questions 2 to 5	Original response code	Item score If Response for question 1 = 0	Item score If Response for question 1 > 0 or missing
None of the time	1	Missing	0
A little of the time	2	Missing	1
Some of the time	3	Missing	2
Most of the time	4	Missing	3
All of the time	5	Missing	4

4 questions are included in the Treatment Satisfaction/Happiness scale score. If 50% (2) or fewer of the 4 questions used in the calculation of Treatment Satisfaction/Happiness score have a missing item score, then the scale score is calculated by multiplying the mean of the non-missing item score by 25. If 3 or

more of the 4 item scores are missing, then the scale score is not calculated and should be missing. Multiplying by 25 transforms the scale score to a 0 to 100 scale, with 0 reflecting the lowest level of satisfaction/happiness with treatment measurable by the scale and 100 reflecting the highest level of satisfaction/happiness with treatment.

2.b Treatment-Related Bother/Inconvenience

Treatment-Related Bother/Inconvenience	Used in calculation of domain score?
6. I was bothered by how often I had to use dry eye treatments	Yes
7. Do you ever use eye drops to treat your dry eyes?	-
8. I was bothered by blurriness shortly after using my eye drops	Yes
9. I was embarrassed when I had to use my eye drops	Yes
10. I felt like I could not go anywhere without my eye drops	Yes

Response for question 7	Original response code	Item score
Yes	1	1
No	2	0

Response for question 6, 8 to 10	Original response code	Item score If Response for question 1 = 0	Item score If Response for question 1 > 0
None of the time	1	Missing	4
A little of the time	2	Missing	3
Some of the time	3	Missing	2
Most of the time	4	Missing	1
All of the time	5	Missing	0

4 questions are included in the Treatment-Related Bother scale score. If 50% (2) or fewer of the 4 questions used in the calculation of Treatment-Related Bother scale score have missing item scores, then the scale score is calculated by multiplying the mean of the non-missing item score by 25. If 3 or more of the 4 item scores are missing, then the scale score is not calculated and should be set as missing. Multiplying by 25 transforms the scale score to a 0 to 100 scale, with 0 reflecting the greatest degree of treatment related bother measurable by the scale and 100 reflecting the lowest degree of treatment-related bother.

Module 3:

Dry eye Symptom bother (20 questions) comprising a unique domain.

Symptom Bother	Used in calculation of domain score?
1.OVER THE LAST TWO WEEKS , how often did you experience dry eye symptoms?	Yes
2. Eyes that felt gritty or sandy	Yes
3. Felt like I needed to close my eyes even though I was not tired	Yes
4. Burning or stinging eyes	Yes
5. Tired eyes	Yes
6. Blurry vision	Yes
7. Itchy eyes	Yes
8. Irritated eyes	Yes
9. Eyes that felt like they had been scratched by something	Yes
10. Eye dryness	Yes
11. Mucus in, around, or coming out of my eyes	Yes
12. Puffy or swollen eyes	Yes
13. Eye redness	Yes
14. Aching or sore eyes	Yes
15. Felt like something was in my eye	Yes
16. Frequent and/or rapid blinking	Yes
17. Difficulty blinking because of little or no moisture in my eyes	Yes
18. Sensitivity to light, glare, and/or wind	Yes
19. Sensitivity to recirculated air (such as air conditioning and heat)	Yes
20. Headaches associated with dry eye symptoms	Yes

Response for question 1	Original response code	Item score
None of the time	1	0
A little of the time	2	1
Some of the time	3	2
Most of the time	4	3
All of the time	5	4

Response for questions 2 to 20	Original response code	Item score
I did not have this symptom / Not applicable	6	0
Not at all	7	1
Slightly	8	2
Moderately	9	3
Very much	10	4

All questions are included in the Symptom Bother scale score. If 50% (10) or fewer of the 20 questions used in the calculation of Symptom Bother scale score have missing item scores, then the scale score is calculated by multiplying the mean of the non-missing item score by 25. If 11 or more of the 20 item scores are missing, then the scale score is not calculated and should be set at missing. Multiplying by 25 transforms the scale score to a 0 to 100 scale, with 0 reflecting the greatest degree of treatment related bother measurable by the scale and 100 reflecting the lowest degree of treatment-related bother.

Change from baseline and from week 8 of above defined subscores will be summarized as a continuous variable at each visit, and mean changes from baseline and from week 8 of all the subscores will be graphically presented (e.g., radar plot) for each visit.

- EQ-5D-5L change from baseline and Week 8 at Month 24 and Month 30

Change from baseline and from week 8 of each dimension score and overall score of health today will be summarized as a continuous variable at each visit, and mean changes from baseline and from week 8 of all the dimension scores will be graphically presented (e.g., radar plot) for each visit.

[REDACTED]

[REDACTED]

[REDACTED]

[REDACTED]

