10.3 STATISTICAL METHODOLOGY

Statistical analysis will be performed by the clinical research organization (CRO) appointed by Dompé.

Appropriate descriptive statistics will be produced by treatment arms according to the nature of the variable. For continuous data, number of observations, mean, standard deviation, median and range (minimum and maximum) and 95% confidence intervals will be presented. For categorical data, frequency distributions and percentages with exact 95% confidence intervals will be presented.

Unless otherwise specified, the significance level used for statistical testing (for descriptive purposes) will be 0.05 and two-sided tests will be used. All patient data collected on the CRF will be listed by patient and center.

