7 DETERMINATION OF SAMPLE SIZE

The sample size for this study is not based on hypothesis-testing and power considerations but is determined by the number of patients from the DEFENDO Study who will rollover to the DEFENDO Long-Term Follow-up Study. The DEFENDO Study enrolled a total of 37 patients.

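### The asymptotic 95% intervals for mean change from baseline, read as mean ± 1.96 SE, would be slightly too narrow with at most 37 patients and can disagree with the t-test beside them

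*SAP*

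**What the plan says.** The interval method for continuous endpoints is set in SAP Section 5, which says that, where appropriate, "the asymptotic 95% confidence intervals of mean change from baseline will be presented as well as p values from one-sample t-test". The same sentence goes on to name a "Wilcoxon signed rank test (depending on the distribution of the data) to compare the observed values vs baseline". The term asymptotic is not defined and no multiplier is given. The sentence names change from baseline only. Several endpoints in that section are also summarised as change from Week 8, with no interval method stated for them.

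The next paragraph of Section 5 specifies exact Clopper-Pearson intervals for proportions. SAP Section 2.8 lists no confidence interval among the summaries for continuous data. Protocol Section 10.3 asks for 95% intervals for continuous data without naming a method, and for tests it says "the significance level used for statistical testing (for descriptive purposes) will be 0.05 and two-sided tests will be used".

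On sample size, SAP Section 7 says "The sample size for this study is not based on hypothesis-testing and power considerations" and sets the ceiling: "The DEFENDO Study enrolled a total of 37 patients". SAP Section 2.5 narrows the set further: "The full analysis set (FAS) will include all enrolled patients who attended either 24-Month Study Visit, or 30-Month Study Visit, or both". Efficacy analyses are "performed based on the observed cases in the FAS population", without imputation.

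**The concern.** A large-sample interval for a mean uses the normal quantile and treats the estimated SD as if it were known. With a few dozen patients or fewer, an interval labelled 95% then covers less than 95%, and the error always makes the estimate look more precise than it is. The t-test in the same sentence uses a different reference distribution, so a table could show an interval that excludes zero next to a p value above 0.05. The outcomes exposed are corneal sensitivity, Schirmer I, TFBUT, BCDVA, the IDEEL subscores and the EQ-5D-5L scores.

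**Working it through.** The documents state no interval width or power figure to reproduce, and 37 is only a rollover ceiling. The check compares the two interval methods directly.

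**Inputs**
- Normal quantile: z = 1.960 (two-sided 0.05, Protocol Section 10.3).
- Maximum n: 37 (SAP Section 7).
- Smaller n: not given, so n = 30, 20, 15 and 10 are assumptions used to show the range.
- SD of the changes: not given and not needed, because it cancels in the width ratio.
- Changes assumed normally distributed.

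**Formulas**, with t* the 0.975 quantile of t on n−1 degrees of freedom:
- Width of the t interval relative to the z interval = t*/1.960.
- True coverage of mean ± 1.960·SD/√n = 1 − 2·P(T > 1.960), with T on n−1 degrees of freedom.
- The z interval excludes zero while the t-test has p > 0.05 when 1.960 < |t| < t*. In p values this runs from 0.05 up to 2·P(T > 1.960).
- Chance of that conflict with no true change = 2·P(T > 1.960) − 0.05. For a non-zero true change it comes from the noncentral t, maximised over the effect.

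**Example, n=37** (36 degrees of freedom): t* = 2.0281, so the ratio is 2.0281/1.9600 = 1.035. The two-sided p value at |t| = 1.960 is 0.0578. Coverage is 1 − 0.0578 = 0.942, and the conflict chance with no true change is 0.0578 − 0.05 = 0.0078.

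| n | t* | t interval wider by | Coverage of z interval | Conflict for p from 0.05 up to | Conflict chance, no true change | Conflict chance, worst case |
|---|---|---|---|---|---|---|
| 37 | 2.028 | 3.5% | 94.2% | 0.058 | 0.8% | 2.6% |
| 30 | 2.045 | 4.4% | 94.0% | 0.060 | 1.0% | 3.3% |
| 20 | 2.093 | 6.8% | 93.5% | 0.065 | 1.5% | 5.0% |
| 15 | 2.145 | 9.4% | 93.0% | 0.070 | 2.0% | 6.8% |
| 10 | 2.262 | 15.4% | 91.8% | 0.082 | 3.2% | 10.5% |

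**Where small n is most likely.** SAP Section 5 sets the IDEEL Work Limitations items to missing for patients who are not working. It sets the treatment satisfaction and treatment bother items to missing for patients who used no dry-eye treatment in the preceding two weeks. These subscores can lose patients by rule, on top of non-return and missed visits.

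**How often a table might show a conflict.** Section 5 describes 16 continuous variables: 4 clinical, 6 IDEEL subscores, 5 EQ-5D-5L dimensions and the health-today score. At two visits that makes 32 comparisons with baseline. If all had an interval and a t-test, and nothing had truly changed, the expected number of conflicting pairs would be 32 × 0.0078 = 0.25 at n=37, or 32 × 0.0148 = 0.47 at n=20. Correlation between outcomes does not alter an expected count. Fewer intervals or t-tests would lower it.

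**The case against.** The strongest reply is that the SAP never writes 1.96. Next to the exact intervals for proportions, asymptotic may be a loose word for not exact, and a t-test stands in the same sentence. The mock shells, a separate document, may settle it. This stands as a caution: the z interval is the natural reading, not a stated formula. It does not remove the need for an edit, because if a t interval is meant, the word used is the wrong one and a programmer could follow it literally.

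A reader might infer that every mean change in the study is affected. The text does not support that: it says where appropriate and covers change from baseline only. A reader might also infer that the intervals are badly wrong. At 37, the only documented figure, the shortfall is 0.8 points of coverage, and the larger effects rest on assumed sample sizes.

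It is also fair to say that little depends on this. SAP Section 2.9 calls all efficacy analyses exploratory, and no success criterion uses these intervals. The primary efficacy objective, corneal epithelial healing, has exact intervals and is untouched. Exploratory status explains why multiplicity is not controlled, but not why an interval labelled 95% should cover less.

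Finally, the coverage figures assume normal changes. EQ-5D-5L dimensions run from 1 to 5 and IDEEL scores from 0 to 100, so a t interval is itself approximate for them. The plan allows for non-normality through the Wilcoxon test, and a t interval need not agree with that p value. This stands as a limit on what the fix achieves.

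**Conclusion.** The concern holds as a minor point. Read as mean ± 1.96 SE, the planned intervals for mean change from baseline under-cover slightly at the maximum sample of 37, and more at smaller samples; the IDEEL work and treatment subscores are the likeliest place for these. Conflict with the t-test is possible but uncommon: with no true change, 0.8% per comparison at n=37 and 3.2% at an assumed n=10.

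This rests on three assumptions: the natural reading of asymptotic, normally distributed changes, and, for every n below 37, a sample size that the documents do not give. The documents do not support a claim that any conclusion of the study would be wrong, since no decision rule uses these intervals.

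**What to change.** In SAP Section 5, keep the where-appropriate qualifier and replace the asymptotic interval for mean change from baseline with: *two-sided 95% confidence intervals of mean change based on the t distribution with n−1 degrees of freedom*. State that the same method applies wherever an interval for change from Week 8 is shown. Where the Wilcoxon test is the one reported, consider pairing it with an interval for the median or pseudo-median change, because the t interval is tied only to the t-test.

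The cost is one phrase, or two with the Week 8 statement, and no new data. Compared with a z interval, intervals become about 3% wider at n=37 and about 15% wider at n=10. Under normal data, coverage returns to 95%. The interval then always agrees with the one-sample t-test at the two-sided 0.05 level.
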